3.2 Patient evaluability

Part 1:

All patients that met the eligibility criteria and take at least one dose of AZD3965 were evaluable for safety decisions.

[figure not shown]
Patients who received less than 75% of their first continuous treatment cycle (for reasons other than toxicity) would not be evaluable for dose escalation decisions. Patients who completed 75% of their first continuous treatment cycle but did not complete the end of Cycle 1 ERG and ophthalmology assessments could also not be evaluable for dose escalation decisions. This was discussed on a per patient basis between the Investigator, Chief Investigator (CI) and CDD.

Part 2:

All patients that meet the eligibility criteria and take at least one dose of AZD3965 will be evaluable for safety decisions.

All patients who meet the eligibility criteria and take at least 75% of their first continuous treatment cycle (28 days) of AZD3965 and have a baseline assessment of disease will be evaluable for response.

To be assigned a status of complete response (CR) or partial response (PR), changes in tumour measurements must be confirmed by repeat measurements performed no less than four weeks after the response criteria are met. To be assigned a status of stable disease (SD), follow-up measurements must have met the SD criteria at least once and at least six weeks after the initial dose of the IMP AZD3965 is given.

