5.5.3 Dose delays

In the event of toxicity, treatment should be delayed for up to two weeks until these toxicities have resolved to Grade ≤ 1 or returned to baseline. If there is no recovery after a two week delay, the patient should be withdrawn from the trial.

Intermittent dosing schedules may be explored based on observed toxicities, PK and PD data.

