5.7.1 Replacement of patients

In **Part 1**, patients were replaced if they fulfilled the following criteria and three evaluable patients had not yet been treated at the same dose level:

• Patients who miss more than 25% of their first AZD3965 cycle (for reasons other than drug related toxicity).

Patients who missed more than 50% of their first AZD3965 cycle due to toxicity which was not dose limiting were discussed between the CDD and CI and a decision will be taken on whether the patient should be replaced by another at the same dose level.

Patients could be replaced if they were unable to complete

as to whether to replace such a patient depended on the status of the other patients within that cohort ERG data already obtained at that dose level. This

decision was made by the CDD in consultation with the CI.

In **Part 2**, patients will be replaced in this phase if they fulfil the following criteria:

• Patients who miss more than 25% of their first AZD3965 cycle (for reasons other than drug related toxicity).

Patients who complete more than 75% of their first AZD3965 cycle (for reasons other than drug related toxicity) but fulfil one of the following additional criteria may also be replaced in Part 2. This will be discussed on a per patient basis between the Investigator, CI and CDD.

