11.2.2 Evaluations during and at Off-study visit

Tumour assessments must be repeated every 2 cycles/8 weeks (Cycles 1-12) and every 3 cycles/ 12 weeks (Cycle 13 onwards) or more frequently, when clinically indicated. All lesions measured at baseline must be measured at every subsequent disease assessment and recorded clearly on the scan reports. All non-measurable lesions noted at baseline must be noted on the scan report as present or absent.

All patients, who are removed from the trial for reasons other than progressive disease, must be re-evaluated at the time of treatment discontinuation, unless a tumour assessment was performed within the previous four weeks.

It is the responsibility of the Principal Investigator to ensure that the radiologists are aware of the requirement to follow-up and measure every target lesion mentioned at baseline and comment on the non-target lesions in accordance with RECIST criteria or the IWG criteria for lymphoma (Appendix 2A and 2B).

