11.3 Tumour response

All patients who meet the eligibility criteria and receive at least 75 % of their first cycle of trial medication and have a baseline assessment of disease will be evaluable for response. To be assigned a status of CR or PR, changes in tumour measurements must be confirmed by repeat measurements performed no less than four weeks after the response criteria are met. To be assigned a status of stable disease (SD), follow-up measurements must have met the SD criteria at least once and at least six weeks after the initial dose of the investigational medicinal product (IMP) AZD3965 is given.

Should rapid tumour progression occur before the completion of 4 weeks, the patient will be classified as having early progression (EP).

Tumour response should be classified as "not evaluable" (NE), only when it is not possible to classify it under another response category, for example, when baseline and/or follow-up assessment is not performed or not performed appropriately.

Expert reviewers appointed by CDD may undertake an independent review of all the Investigator's assessed objective responses (CR and PR). The expert reviewers will include at least one specialist who is not an Investigator in the trial. In case of disagreement between the Investigator's and the expert

reviewers' assessment, discussion will take place between the two parties in order to reach a consensus. However, if it is not forthcoming, the assessment of the expert reviewers will be retained in the clinical study report. The eCRF will reflect the Investigator's opinion.

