14.5 Anti-tumour activity

Documenting anti-tumour activity is a secondary objective of this trial. Patients must receive at least 75% of their first cycle of the trial medication to be evaluable for response. Objective responses, the best tumour response achieved by each patient while on trial and the time to progression will be presented in the data listings.

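### The Part 2 response-evaluable set drops, and Section 5.7.1 replaces, patients who progress or die before receiving 75% of Cycle 1

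*Protocol*

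**What the plan says.** The 75% condition for response evaluability appears three times in the protocol.

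- Section 3.2 (Part 2) requires that eligible patients "take at least 75% of their first continuous treatment cycle (28 days) of AZD3965 and have a baseline assessment of disease".
- Section 11.3 repeats this in nearly the same terms.
- Section 14.5 states: "Patients must receive at least 75% of their first cycle of the trial medication to be evaluable for response".

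None of these makes an exception for progression, death or toxicity. By contrast, the Part 1 rule on evaluability for dose escalation in Section 3.2 does exempt toxicity.

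Section 5.7.1 makes replacement in Part 2 mandatory for "Patients who miss more than 25% of their first AZD3965 cycle (for reasons other than drug related toxicity". Drug-related toxicity is the only exemption. Section 5.7 lists progression among the reasons for ending treatment.

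Two other provisions bear on early failures. Section 11.3 says: "Should rapid tumour progression occur before the completion of 4 weeks, the patient will be classified as having early progression (EP". It also allows the not-evaluable category "only when it is not possible to classify it under another response category". Section 11.3.2 defines early death as death in the first 28 days. Neither section says that these patients belong to the evaluable set.

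The Part 2 secondary endpoint (Sections 1.2.2 and 3.1.2) counts stable disease as well as partial and complete response. For presentation, Section 14.5 says that "the best tumour response achieved by each patient while on trial and the time to progression will be presented in the data listings". It names no rate and no denominator.

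**The concern.** Membership of the response set depends on what happens after the first dose. Early progression and early death are among the outcomes the endpoint is meant to capture, yet before the 75% mark they remove the patient from the set. Replacement then fills the place with someone who lasted longer. The selection favours the drug, and recruiting more patients under the same rule would not remove it.

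The rule also divides the early-progression category by dosing. Two patients who both progress within four weeks can fall on opposite sides of the set boundary because of a single day's dose.

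Toxicity is a separate matter. Section 5.5.3 provides that "In the event of toxicity, treatment should be delayed for up to two weeks until these toxicities have resolved". A patient who uses most of that allowance within Cycle 1 fails the 75% condition, yet may resume and respond. Leaving such patients out can move a rate in either direction.

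At stake is the credibility of any activity figure quoted for DLBCL and Burkitt lymphoma from the set that the protocol calls evaluable.

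**Working it through.** The protocol gives no target rate, power calculation or early-loss allowance for Part 2, so there is no stated figure to reproduce. The inputs are the 28-day cycle, the 75% rule, the ceiling of 20 evaluable patients (Section 3.3) and the replacement rule (Section 5.7.1). The numbers of early losses and of responders are assumptions.

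**Threshold.** 0.75 × 28 = 21 days of dosing. With uninterrupted dosing, a last dose on Day 20 gives 20/28 = 71.4% (outside the set). A last dose on Day 21 gives 21/28 = 75.0% (inside).

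**Who is in, and who is replaced.**

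| Patient | In response set? | Replaced? |
|---|---|---|
| Progresses, last dose Days 1–20 | No | Yes |
| Dies of lymphoma, last dose Days 1–20 | No | Yes |
| Drug-related death, last dose Days 1–20 | No | No |
| Progresses, last dose Days 21–27 | Yes | No |
| Drug-related toxicity break of 8–14 days, all within Cycle 1 | No | No |

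Patients in the first three rows cannot be successes. Stable disease must be shown at least six weeks after the first dose, and complete or partial response must be confirmed at least four weeks later (Section 3.2).

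**Early losses that are replaced.** Let k be the number replaced and x the number of successes among 20 evaluable patients. The k patients add nothing to the numerator, so the set gives x/20, all treated gives x/(20 + k), and the inflation factor is (20 + k)/20.

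| k | Share of treated, k/(20 + k) | Factor | CR+PR, x = 4: set vs treated | CR+PR+SD, x = 8: set vs treated |
|---|---|---|---|---|
| 1 | 1/21 = 4.8% | 1.05 | 20.0% vs 4/21 = 19.0% | 40.0% vs 8/21 = 38.1% |
| 2 | 2/22 = 9.1% | 1.10 | 20.0% vs 4/22 = 18.2% | 40.0% vs 8/22 = 36.4% |
| 5 | 5/25 = 20.0% | 1.25 | 20.0% vs 4/25 = 16.0% | 40.0% vs 8/25 = 32.0% |

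Five losses is a high-end assumption. Entry requires a life expectancy of at least 12 weeks (Section 4.1.1), and the first scheduled tumour assessment is at about week 8 (Section 11.2.2). Only death, early stopping, or progression evident without a scheduled scan can count.

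For scale, the exact (Clopper–Pearson) 95% interval is 5.7% to 43.7% for 4/20 and 4.5% to 36.1% for 4/25.

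**Toxicity breaks.** Take a break wholly inside Cycle 1. Seven days leaves 21/28 = 75.0% (in), 8 days leaves 20/28 = 71.4% (out), and 14 days leaves 14/28 = 50.0% (out). Suppose 20 patients are treated, 2 have such breaks and are not replaced, and 4 of the other 18 respond. The set gives 4/18 = 22.2%. The rate among all treated is:

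- neither of the 2 responds: 4/20 = 20.0% (set too high);
- one responds: 5/20 = 25.0% (set too low);
- both respond: 6/20 = 30.0% (set too low).

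**The case against.** The strongest reply is that the bias belongs to an estimate the protocol does not plan. Section 14.5 commits to listings, and no rate, target or decision rule is stated. An SAP, not seen here, may set the denominator. Early failures are also visible: they carry the early-progression or early-death label, the listing of best response covers each patient, and Section 14 puts all treated patients' data into the primary analysis report. A reader could rebuild the all-treated denominator. The primary objectives, dose and safety, are untouched, and the assumed shifts are small.

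All of this limits the consequence, but it does not remove the defect. The protocol did not leave the set open. It fixes the set three times and ties replacement to nearly the same threshold, so an SAP would have to depart from the protocol to repair it. A label in a listing does not place a patient in the set. The protocol's own RECIST appendix (Appendix 2A, Section 2.4.4) asks that early progression, early death and inevaluability be clearly described in each protocol. The text missing from Section 5.7.1 concerns patients who completed more than 75% of Cycle 1, so it cannot cover those at issue.

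Two narrower points stand. Not every early progression or death is left out, only those below the dosing threshold. The toxicity case also requires the break to fall within Cycle 1, and it shows no consistent direction.

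**Conclusion.** The concern holds. As written, the Part 2 response set excludes patients who progress or die before receiving 75% of Cycle 1, and it replaces them unless drug-related toxicity was the cause. A response or disease-control rate on that set would be too high by a factor of (20 + k)/20. That is 1.05 to 1.25 for 1 to 5 replaced early losses, or 1 to 4 percentage points on a 20% rate and about 2 to 8 points on a 40% rate. The number of early losses is assumed, because the protocol gives none.

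The shifts lie within sampling error at this sample size, the endpoint is secondary, and no test, error rate or dose decision depends on it. The bias matters only if a rate is calculated, but the set labelled evaluable for response is the natural denominator for one. It should be corrected because it is systematic and cheap to remove. Exclusions for toxicity breaks add a second distortion of unknown direction.

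**What to change.** **Sections 3.2, 11.3 and 14.5.** Make the main denominator for any response or disease-control rate all eligible Part 2 patients who took at least one dose and have a baseline disease assessment. The baseline condition is harmless because it is settled before treatment. Count early progression, early death, early stopping without a documented response, and not evaluable as non-response. Let patients who interrupt and resume keep their actual best response. Keep the 75% set as a supportive analysis.

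**Section 5.7.1.** State that replaced patients stay in the main denominator.

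**Cost.** Protocol wording and one extra tabulation. No additional patients or assessments are needed: Sections 8.4 and 11.2.2 already call for tumour assessment at progression or on stopping treatment, unless one was done in the previous four weeks. The reported rate is likely to be somewhat less favourable.

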3.3 Design of the clinical trial

This is a multi-centre, Phase I, dose escalation trial in two parts.

Part 1

In Part 1, a total of 42 patients with advanced solid tumours were recruited into Part 1 of the study, 40 of which received AZD3965.

At each dose level, up to six evaluable patients were treated on Day -7 followed by continuous daily dosing starting on Day 1. One treatment cycle was 28 days. In Part 1, Cycle 1 includes the additional dosing day at Day -7.

The starting dose was 5 mg given as an oral capsule. Pharmacokinetic assessments were performed during this cohort to assess the half-life of AZD3965 in order to inform whether dosing for future cohorts should be once or twice daily.

The next total daily dose level was planned to be 10 mg either once daily or split into two daily doses.

The total daily dose was doubled in successive cohorts until an NCI CTCAE Version 4.02 Grade 2 highly probably or probably related adverse drug reaction was reported. Subsequent dose increases between cohorts were up to a maximum of 50% driven by reported safety, PK and PD data. The decision to continue with dose escalations was based on drug exposure as measured by PK assessments during Cycle 1 and PD effects. Drug exposure did not exceed the maximum exposure limit as set out in Section 5.2. If PK data from Cycle 1 indicated that the exposure cap had been exceeded, the cohort would have been completed but no further dose escalations would have take place.

If continuous daily dosing was not tolerated at levels that inhibit MCT1 then intermittent schedules would be explored.

Up to six evaluable patients were treated at each dose level.

If a DLT was observed

then the cohort was expanded to six patients. In the event of a gender specific DLT, at least one further patient of that gender would have been enrolled into an expanded cohort of at least six patients. If a second DLT was reported, a dose level below would have been expanded to six evaluable patients to identify the MTD.

An interval of 14 days (from Day -7 (7 days from Day 1) was observed between the recruitment of the first and second patients in a cohort. The second, third, fourth, fifth and sixth patients could be treated in parallel. Twenty-eight days (from Day 1) of data (safety, PK and PD) was available for a minimum of three evaluable patients in a cohort in order to make the decision to dose escalate. The following cohorts and doses were explored:

Cohort Number	Dose
1	5 mg once daily (OD)
2	10 mg OD
3	20 mg OD
4	30 mg OD
5	15 mg twice daily (BD)
6	10 mg BD

Part 2

In Part 2, up to 20 evaluable patients with DLBCL or BL will be treated at the RP2D from Part 1 of the study. There will be no administration of AZD3965 on Day -7 in Part 2 of the study. AZD3965 will be administered as continuous daily dosing in 28 day cycles starting from Cycle 1 Day 1 for up to six cycles. If the patient has not progressed after six cycles, further cycles may be given after discussion between the Investigator and the CDD and written approval given by the CDD, refer to Section 5.7. In the case of toxicity, treatment will be interrupted and then resumed when all toxicities have returned to Grade 1 or lower. Intermittent dosing schedules may be explored based on observed toxicities.

An interval of 14 days (from Cycle 1 Day 1) must be observed between the recruitment of the first and second patient in the expansion cohort but subsequent patients can be treated in parallel. Data must be available (safety and PK) for a minimum of three evaluable patients in order to make any decision to change the Part 2 dose (RP2D). Any changes to the Part 2 dose (RP2D) will be for safety reasons and to decrease the total daily dose only.

The study was designed in accordance with the EMEA Guideline on strategies to identify and mitigate risks for first-in-human clinical trials with investigational medicinal products.

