In both Parts 1 and 2, AZD3965 will be administered as continuous daily dosing in 28 day cycles for up to six cycles. If the patient is benefitting from the treatment, a further six cycles may be administered after discussions between the Investigator and the Sponsor, Cancer Research UK's Centre for Drug Development (CRUK CDD). In the case of toxicity, treatment will be interrupted and then resumed when all toxicities have returned to Grade 1 or baseline. Intermittent dosing schedules may be explored based on observed toxicities.

In Part 2 all patients will be treated at the RP2D determined in Part 1. There will be no Day -7 dose in Part 2. All patients in Part 2 will be treated at the RP2D as continuous daily dosing in 28 day cycles for up to six cycles starting on Day 1. If the patient has not progressed after six cycles, further cycles may be given after discussion between the Investigator and the CDD (see Section 5.7).

An interval of 14 days (from Cycle 1 Day 1) must be observed between the recruitment of the first and second patient in the expansion cohort but subsequent patients can be treated in parallel. Data must be available (safety and PK) for a minimum of three evaluable patients in order to make any decision to change the Part 2 dose (RP2D). Any changes to the Part 2 dose (RP2D) will be for safety reasons and to decrease the total daily dose only.

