3.1.3 Tertiary objectives and endpoints

3.1.4 Definition of dose limiting toxicity

The DLT and MTD are defined using the NCI CTCAE Version 4.02.

Only DLTs identified during Part 1 Cycle 1 (including Day-7 in Part 1) informed the decision to dose escalate through the increasing dose levels. Dose limiting toxicities will be defined throughout the treatment period and will be considered in determining the RP2D for Part 2.

Any DLTs experienced during Part 2 will be collected to assist with assessment of adverse events (AEs) and patient safety profiles and the dose may be adjusted accordingly. Any changes to the Part 2 dose (RP2D) will be for safety reasons and to decrease the total daily dose only.

A DLT is defined as highly probably or probably drug related:

Haematological:

- neutropenia Grade 4 for \geq 5 days duration
- febrile neutropenia (fever of unknown origin without clinically or microbiologically documented infection) with Grade 3 or 4 neutropenia (absolute neutrophil count ANC <1.0x10⁹/L and fever ≥38.5°C)
- infection (documented clinically or microbiologically) with Grade 3 or 4 neutropenia (ANC <1.0x10⁹/L)

• thrombocytopenia Grade 4: a) for ≥5 days*, or b) associated with active bleeding, or c) requiring platelet transfusion.

Cardiac:

- QTc interval >500 msec or an increase of >60 msec from baseline (verified manually (Fridericia's correction (QTcF))
- Any other Grade 3 or 4 cardiac toxicity excluding Grade 3 hypertension
- Non-sustained ventricular tachycardia (<30s) associated with syncope or pre-syncope
- Sustained ventricular tachycardia (≥30s) with or without symptoms
- Ejection Fraction (EF): ≥20% reduction in left ventricular ejection fraction (LVEF) to below the lower limit of normal (<50% on echocardiography)

Ophthalmic:

Part 1:

- 25% (or more) reduction on electroretinography (light and dark adapted) which does not resolve to baseline or 25% (or less) within 2 weeks following dose delay
- 50% (or more) reduction on electroretinography (light and dark adapted)

Part 2:

- 25% (or more) a- wave reduction on electroretinography (light and dark adapted) which does not resolve to baseline or 25% (or less) within 2 weeks following dose delay
- 50% (or more) a wave reduction on electroretinography (light and dark adapted)
- 50% (or more) b- wave reduction on electroretinography (light and dark adapted) which does not resolve to baseline or 50% (or less) within 2 weeks following dose delay

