5.3 Dosing schedule/treatment schedule (Parts 1 and 2)

For Part 1 of the study, AZD3965 was administered orally on Day -7 and then continuously for a 28 day cycle starting on Day 1.

For Part 2 of the study, AZD3965 will be administered orally continuously for a 28 day cycle starting on Cycle 1 Day 1. There will be no administration of AZD3965 on Day -7 in Part 2 of the study.

In Part 1, the total daily dose was initially administered once daily and was reviewed throughout Part 1, the total daily dose was spilt into a twice daily dosing schedule.

In both Part 1 and 2 a maximum of six cycles will be administered (further cycles can be given upon review of the data and approval by CRUK CDD where patients are benefiting from receiving AZD3965 i.e. tumour assessments show a stable or partial/complete response, refer to Section 5.7).

The AZD3965 capsules must be swallowed whole (with water) and not chewed, crushed, dissolved or divided.

Patients in Part 1 were instructed to take AZD3965 with food, except for their first dose at Day -7 which was taken fasted. In Part 2 as there is no Day -7 dose, AZD3965 is to be taken with food and should be taken at the same time(s) every day.

For the once daily dosing in Part 1, the total daily dose of AZD3965 was taken at the same time once a day, and for twice daily dosing, the total daily dose of AZD3965 was spilt into two doses and should be taken in the morning and 12 hours later, respectively.

In Part 2 a twice daily dosing is planned unless emerging data suggests a once daily dosing is indicated.

On the days of PK sampling (see Section 9.4.1) patients should take their scheduled dose at the hospital so that the exact time of administration can be recorded.

In cases of toxicity, treatment may be interrupted and then resumed when all toxicities have returned to Grade 1 or lower. In the event of Grade 3 or 4 QTc prolongation (QTc interval >500 msecs or increase of > 60 msecs from baseline (QTcF correction)), treatment with AZD3965 will be withdrawn.

Intermittent dosing schedules and administration with or without food may be explored based on observed toxicities or if continuous daily dosing is not tolerated at levels that inhibit MCT1.

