5.4 Dose escalation scheme (Part 1)

Each patient cohort included a maximum of six evaluable patients following a rolling six dose escalation scheme (Skolnik A.M. *et al.*, 2008).

The starting dose was 5 mg given as an oral capsule. 5, 10, 20, and 30 mg capsules can be manufactured. Pharmacokinetic assessments were performed during this cohort to assess the potential half-life of AZD3965 in order to inform whether dosing for future cohorts should be once or twice daily. The next total daily dose level will be 10 mg either once daily or split into two daily doses.

The total daily dose was doubled in successive cohorts until an NCI CTCAE Version 4.02 Grade 2 highly probably or probably related adverse drug reaction was reported. Subsequent dose increases between cohorts was up to a maximum of 50% driven by reported safety, PK and PD data. If continuous daily dosing is not tolerated at levels that inhibit MCT1 then intermittent schedules will be explored.

A maximum of six evaluable patients were treated at each dose level with at least one male patient in each cohort. It is acceptable that the fourth, fifth and sixth patients can begin treatment at the same time as the second and third patients which must be after the first patient has completed Cycle 1 Day 7 of treatment although this will be assessed and confirmed by the CDD based on emerging data from the study.

The dose level of AZD3965 was assigned according to the number of patients already enrolled at the current dose level, the number of DLTs (and any other drug-related AEs) observed at the current dose level and the number of patients enrolled who are at risk of developing a DLT (see Section 3.2 Definition of dose limiting toxicity). When sufficient data, as deemed by the Sponsor and CI, was available to assess these, the AZD3965 dose level was assigned according to the following:

- If the data is available from a minimum of three patients who have been treated in a cohort and no DLTs have been observed at that dose level, then dose escalation can be considered.
- If the data is available from three patients who have been treated in a cohort and one DLT has been observed at that dose level, then the cohort will be expanded to include at least 6 patients.
- If two DLTs have been observed at any dose level, the dose will be de-escalated and the
 previous total daily dose level will be expanded to include up to six patients. If the previous total

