5.4.2 Expansion of dose level(s)

If one instance of DLT (as defined in Section 3.1.3) was observed in three patients, at least six evaluable patients would be treated at that dose level. If one out of six patients experienced a DLT, dose escalation would continue. If two out of up to six (i.e. between two and six) patients experience a DLT dose escalation would stop and this dose would be defined as the maximum administered dose (MAD). At least six patients would be treated at the total daily dose level below the MAD to define the MTD.

The MAD could also equal the MTD in the event that dose escalation was stopped before two DLTs were observed at a given dose level, due to the expectation that higher dose levels would be too toxic to administer to patients.

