5.5.2 Dose reductions

In Part 1 the dose of AZD3965 would be reduced to the previous dose level for any patient who experienced a DLT (with the exception of QTc prolongation, these patients would be withdrawn from the trial, see Section 5.5.1). If a patient had a dose reduction, their dose would not be re-escalated.

Treatment at the reduced dose would start when the toxicities had resolved to Grade ≤1 or returned to baseline (if within 14 days).

If the patient experienced the same or different DLT toxicity again at this reduced dose, there would be no further dose reductions and the patient was withdrawn from the study.

In Part 2, the PK profile of AZD3965 and patient safety data will be reviewed after the first three evaluable patients. Following this review, the RP2D may switch to once or twice daily dosing (at the same total daily dose level) or a lower total daily dose at the discretion of the CDD and CI. Any DLTs experienced during Part 2 will be collected to assist with assessment of patient safety profiles and the RP2D may be adjusted accordingly.

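### The Part 2 dose-change rule puts a three-patient data minimum on safety reductions with no stated DLT exception, and conflicts with Sections 5.3 and 5.5.2 on once/twice-daily switches

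*Protocol*

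**What the plan says.** **Minimum data.** Section 3.3 (Part 2) states: "Data must be available (safety and PK) for a minimum of three evaluable patients in order to make any decision to change". What is being changed in that sentence is the RP2D. Section 1.4 has the same requirement: "Data must be available (safety and PK) for a minimum of three evaluable patients".

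**Permitted change.** Section 3.3 continues: "Any changes to the Part 2 dose (RP2D) will be for safety reasons and to decrease the total daily dose only". Sections 1.4 and 3.1.4 repeat this limit.

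**DLTs in Part 2.** Section 3.1.4 says that DLTs are collected to help assess "patient safety profiles and the dose may be adjusted accordingly". The last sentence of Section 5.5.2 says the same of the RP2D. Neither gives a number of DLTs or a time, and neither mentions the three-patient minimum.

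**Schedule.** Section 5.3 states: "In Part 2 a twice daily dosing is planned unless emerging data suggests a once daily dosing is indicated". Section 5.5.2 plans a PK and safety review after three evaluable patients. After that review the sponsor's drug development centre and the chief investigator may switch the RP2D between once and twice daily at an unchanged total daily dose, or lower the total.

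**Part 1, for comparison.** Section 5.4: "If two DLTs have been observed at any dose level, the dose will be de-escalated". Section 5.4.2: "If two out of up to six (i.e. between two and six) patients experience a DLT dose escalation would stop". The individual reduction rule in Section 5.5.2 is also limited to Part 1: "In Part 1 the dose of AZD3965 would be reduced to the previous dose level for any patient who experienced a DLT".

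**The concern.** A minimum number of patients normally guards against raising a dose on too little evidence. Part 1 used it that way: three patients to escalate, two DLTs to come down. In Part 2 the total daily dose can only fall, so the same kind of minimum now sits in front of reductions. A site or sponsor team following Sections 1.4 and 3.3 to the letter would find two DLTs in two patients insufficient to lower the dose for the cohort, and would need PK results as well.

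The second problem is a plain conflict. Three sections allow a change only if it lowers the total daily dose, and two allow a schedule switch that leaves it unchanged. Section 5.5.2 calls that switch a change of the RP2D, the same term that the restrictive sentence uses. A reader of Section 3.3 alone would think the switch barred. A reader of Section 5.5.2 would think it authorised.

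**Working it through.** The protocol gives no DLT threshold, boundary or operating characteristic for Part 2, so there is no figure to reproduce. The check is a comparison of texts, followed by simple arithmetic on how often the problem could arise.

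**Step 1: what the minimum covers.** Sections 1.4 and 3.3 apply it to every decision to change the Part 2 dose. The only change those sections permit is a safety decrease. The minimum therefore covers safety decreases, and no exception is stated.

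**Step 2: what "evaluable" means for a reduction.** Section 3.2 (Part 2) makes a patient evaluable for safety decisions after one dose. The 75%-of-first-cycle criterion is for response. A reduction for safety is a safety decision, so one dose suffices. Part 2 PK sampling ends 24 hours after the first Cycle 1 Day 1 dose (Section 9.4.1).

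**Step 3: shortest time.** Count the first patient's first dose as day 1.
- Section 3.3 requires 14 days between patients 1 and 2 and lets later patients start in parallel. Patients 2 and 3 can start on day 1 + 14 = 15.
- The third patient's 24-hour sample falls on day 15 + 1 = 16.
- The data requirement is thus met one day after the third patient's first dose, plus PK turnaround, which is not stated.

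The main cost of the literal rule is therefore one more patient exposed at the same dose and a dependence on PK results, rather than a long wait.

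**Step 4: how often.** With true DLT rate p and independent patients, P(DLT in both of the first two) = p². No Part 2 rate is given, so the rates are assumptions. The value 1/6 is taken from the one-in-six ceiling in the primary endpoint (Section 3.1.1).
- p = 1/6: (1/6)² = 0.028, or 2.8%
- p = 1/3: (1/3)² = 0.111, or 11.1%
- p = 1/2: (1/2)² = 0.25, or 25%

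These are upper limits. The problem also requires both DLTs to be known before the third patient starts; if patient 3 starts alongside patient 2, the patient count is already met.

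**Step 5: the schedule switch.** Section 3.3 lists two twice-daily cohorts. 2 × 10 mg = 20 mg a day, which was also given once daily (cohort 3). 2 × 15 mg = 30 mg a day, also given once daily (cohort 4). Section 3.3 reports that exposure stayed within the limit. Harm from a switch between these is therefore limited, and the defect is the contradiction.

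**The case against.** The strongest reply is that the protocol already contains a DLT route. In Section 5.5.2 the three-patient review and the DLT sentence are separate, and the latter carries no patient count; Section 3.1.4 agrees. Earlier adjustment was probably intended. This stands in part: it makes the text inconsistent rather than a firm ban, but nothing says which sentence prevails.

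Other safeguards also remain:
- interruption for toxicity, and withdrawal if there is no recovery in two weeks (5.5.3);
- mandatory withdrawal for defined QTc and ERG changes (5.5.1, Appendix 4);
- intermittent dosing;
- termination or temporary halt (13);
- urgent safety measures (10.6).

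The sponsor may also hold recruitment. All this stands and limits the harm. Interruption and withdrawal, however, act on affected patients and do not reset the dose for the next one.

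A minimum also has a legitimate use: it stops a reduction resting on chance events when no route back up exists. That is a fair cost, and it is acknowledged in the fix.

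On the switch, the restrictive sentence can be read as fixing only the direction of the total daily dose. That reading is reasonable, but the wording should say so.

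Three stronger inferences are tempting and not supported:
- *Reductions are delayed by weeks.* The 75% criterion belongs to response, and a gap while a third patient is being recruited doses no one new.
- *Two of two shows the true rate is above 1/6 (16.7%).* The exact one-sided 95% lower limit is √0.05 = 22.4%, but the two-sided limit is √0.025 = 15.8%. Both ignore the Part 1 experience behind the RP2D.
- *Nothing can be done after two early DLTs.* The safeguards above show otherwise.

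**Conclusion.** The point holds as an inconsistency with a limited safety consequence. Sections 1.4 and 3.3 attach a three-patient safety and PK minimum to a change that can only be protective, without a DLT exception, and Sections 3.1.4 and 5.5.2 leave open whether it is waived. Followed literally, Part 2 is slower to reduce than Part 1 was: after two DLTs in two patients, a cohort-level reduction needs a third patient given at least one dose at the same RP2D, with 24-hour PK, or else an urgent safety measure, halt or amendment.

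The chance of arriving there is at most 2.8% at a true DLT rate of 1/6 and 11% at 1/3. Both rates are assumed, and patients are taken as independent. The situation is uncommon at an acceptable dose and likelier at one that is too toxic, which is when the rule matters.

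The conflict over once/twice-daily switching is separate, rests on the text alone and needs no assumption. Both should be corrected; neither shows that patients would go unprotected.

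**What to change.** Put one rule in Sections 1.4, 3.1.4, 3.3 and 5.5.2, and refer to it from 5.3:

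*The total daily dose will not be increased. A reduction for safety may be made at any time, with no minimum number of patients or PK data. A once/twice-daily switch at the same total daily dose may be made after safety and PK review of three patients evaluable for safety, to a dose and schedule tested in Part 1.*

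This keeps the planned three-patient review for the decision it suits, names the Section 3.2 definition that applies, and removes the conflict over switching. It costs a few sentences in an amendment and adds no visit or assessment.

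The downside is that a reduction could rest on one or two chance events and could not be reversed. At a true rate of 1/6, two DLTs in two patients would still occur 2.8% of the time. The wording permits a reduction without forcing it, so the sponsor and the chief investigator keep that judgement.
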